## 5.1.7 Blood Pressure, Pulse Rate, Body Temperature, Height, and Body Weight

Data on blood pressure, pulse rate, body temperature, and body weight will be collected at the time points specified in Table 1 and Section 5.1.10. Height will measured only during the screening period to calculate predicted FVC, an exclusion criterion.

Blood pressure and pulse rate will be measured after the subject is confirmed to be at rest in a supine or sitting position for several minutes, and the measurement on the efficacy evaluation day will be performed before the evaluation. Pulse rate, blood pressure, and body temperature will always be measured at the same site of the same arm whenever possible. The measurement will be immediately repeated if any abnormality is observed. Any clinically significant change from baseline will be recorded as an adverse event specified in Section 12.1.

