## 5.1.9 Laboratory Values

The investigator or subinvestigator must evaluate all laboratory values to determine whether they are clinically significant events.

Laboratory tests will be performed while subjects are at rest and fasted whenever possible. The measurement on the efficacy evaluation day will be performed before the evaluation.

Any laboratory value determined to be clinically significant shall be followed up and reported as an adverse event specified in Section 12.1. In addition, the laboratory value will be repeatedly evaluated until the value resolves to baseline level or becomes resolving, or is determined to be difficult to follow-up due to a reason described in Section 12.1.7, "Follow-up of Adverse Events."

Outline of the laboratory parameters is shown in Table 5-1.

As shown in Section 11.7.1, only the serum CK concentration during the hospitalization period will be used for the efficacy evaluation.

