# 7.1.2.1 Dose Suspension/Resumption Criteria

The dose suspension/resumption criteria are shown in Table 7.1.2.1-1. The dose of the investigational product will be suspended or resumed according to the criteria below. The rationale for the dose suspension criteria is described in Section 14.9.

- (1) Dose suspension/resumption procedures
  - The investigator or subinvestigator must suspend the dose if any adverse event specified in Table 7.1.2.1-1 occurs.
  - After dose suspension, an early subject visit other than the visits specified in this protocol will be scheduled to confirm whether the adverse event is resolved or resolving, for the earliest possible dose resumption.
  - Even if the resumption criteria is met, however, the dose cannot be resumed if prolonged dose suspension is determined to be necessary by the investigator or subinvestigator for the safety of the subject.
  - The dose may be suspended even in the absence of any adverse event specified in Table 7.1.2.1-1 if the dose suspension is determined to be necessary by the investigator or subinvestigator due to any other adverse event.
  - Any dose suspension determined by the investigator shall be recorded with the detailed medical reason/rationale in the source documents.
  - Dose suspension determined by the investigator due to the subject's complaint of the number of tablets to be taken will not be permitted.

Item	Dose suspension criteria	Dose resumption criteria
Adverse event	Onset of the following symptoms of glucocorticoid deficiency (severity: any): Hyponatraemia (< 130 mEq/L), hypoglycaemia (< 50 mg/dL), and orthostatic hypotension	Hyponatraemia, hypoglycaemia: Resolved to the baseline level or site reference level and orthostatic hypotension: resolved
Onset of seve	Onset of severe adverse events a	Resolving to mild or lower in severity

Table 7.1.2.1-1 Dose Suspension/Resumption Criteria

a Excluding cases in which the relationship with the investigational product is definitely ruled out [e.g., injury associated with the motor function disorder due to DMD (underlying disease), including fractures, sprain, bruise, and contusion]

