## **3.4.2** HANDLING OF MISSING VALUES AND ABNORMAL VALUES

For missing values, no imputation will be applied. Data employed at each time point will be used in analysis. For primary and secondary efficacy endpoints, LOCF or MMRM imputation will be applied as needed. The incidence of adverse events, etc. will be analyzed using the analysis set as the denominator.

All measurement data will be used in analysis, except for abnormal values that can be clearly explained, including laboratory values affected by hemolysis at blood collection. Any abnormal value excluded from analysis will be identified, and the rationale for exclusion will be provided.

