## **4.2** Criteria for Handling in Analysis

- If it is questionable as to how some subject data are to be handled, the sponsor will discuss the case(s) with the medical expert to make a decision before key code breaking.
- Data from subjects who have been administered the investigational product different from their randomized investigational product will be handled as data for the actually administered investigational product in the analysis of treated patients or PPS.
- In the analysis of FAS, the data will be handled as data for the randomized investigational product.
- Evaluation made in the period other than the period of clinical assessments stipulated in the protocol will be excluded as a rule (Table 4.2). If the evaluation is included in the analysis, the fact should be stated clearly. If examination is conducted twice or more during the period, the examination closest to the stipulated date will be adopted.

Table 4.2 Termissible Range for Chinear Assessments		
Stipulated days	Permissible range	
Baseline period	Within 2 weeks after enrollment	
Day4	±1 day	
Day6	Day 6 only	
Day15	+5 days*	
Day29	$\pm 5$ days	
Day57, Day127	±7 days	
Day85, Day169	±7 days	
Follow-up period (21 days after the end of investigational product administration)	±7 days	

Table 4.2 Permissible Range for Clinical Assessments

\* If all the days in the permissible range are holidays/national holidays and clinical assessments cannot be performed, the first working day after the holidays/national holidays is permitted.

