## (4) 12-lead ECG

For QTc interval, a test parameter of 12-lead ECG, Fridericia's formula will be used.

- For QTcF interval and heart rate, summary statistics of measured values at each evaluation time point will be calculated.
- For QTcF interval and heart rate, summary statistics of the change from immediately before Day 1 dose in measured values at each evaluation time point after start of the dose will be calculated.
- The QTcF interval at each evaluation time point will be categorized into "≤450 msec, > 450 msec and ≤480 msec, > 480 msec and ≤500 msec, and > 500 msec" before frequency tabulation.
- The change in QTcF interval from the value immediately before Day 1 dose to each time point of evaluation will be categorized into "≤30 msec, > 30 msec and ≤60 msec, and > 60 msec" before frequency tabulation.

- The proportion of subjects with abnormal change in 12-lead ECG (patients for whom the result is judged to be "Abnormal with clinical significance") and the 2-sided 95% confidence interval will be calculated. A list of subjects with abnormal change in 12-lead ECG will also be created.
- (5) Body weight, blood pressure, pulse rate, and body temperature
  - For body weight, systolic blood pressure, diastolic blood pressure, pulse rate, and body temperature (axilla), summary statistics at each evaluation time point will be calculated.
  - For body weight, blood pressure and pulse rate, summary statistics of the change from immediately before Day 1 dose at each evaluation time point will be calculated.
- (6) Cardiac ultrasonography (echocardiography)
  - For left ventricular EF and left ventricular FS, summary statistics at each evaluation time point will be calculated.
  - For left ventricular EF and left ventricular FS, summary statistics of the change from the baseline value measured in the screening period at each evaluation time point will be calculated.
  - The incidence of the cases with abnormalities on echocardiography (patients for whom Clinical Significance was judged to be "Yes") and 2-sided 95% confidence interval will be calculated.

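### SAP 4.2 does not exempt safety data from its visit-window and closest-date rules, so by-time-point safety summaries omit unscheduled and some repeat tests by default

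*SAP*

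**What the plan says.** SAP 4.2 sets two rules tied to the windows in its Table 4.2.

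- Timing: "Evaluation made in the period other than the period of clinical assessments stipulated in the protocol will be excluded as a rule". An exception is allowed without criteria: "If the evaluation is included in the analysis, the fact should be stated clearly".
- Multiplicity: "If examination is conducted twice or more during the period, the examination closest to the stipulated date will be adopted".

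Neither rule is limited to efficacy. SAP 3.4.2, repeating Protocol 13.1.2.2, takes a different line: "All measurement data will be used in analysis, except for abnormal values that can be clearly explained".

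The numerical safety outputs in SAP 6.2.2 are organised by time point. For ECG, "The QTcF interval at each evaluation time point will be categorized into" four bands, and the change in QTcF from before the Day 1 dose is banded in the same way. Laboratory values, vital signs, and left ventricular EF and FS get summary statistics at each evaluation time point. The section describes no summary of the worst value after the first dose and no rule for unscheduled tests.

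**The concern.** The protocol creates off-schedule safety tests when something has gone wrong or needs checking. One closest value per visit is a sensible convention for by-visit means. It is a poor rule for outputs meant to show extremes, such as QTcF bands, if an extreme reading was taken outside a window or was the further of two readings inside one.

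This matters here because Protocol 1.3.2 says that the high dose has never been given in clinical studies and that its tolerability is not yet shown. The planned size is 11 boys per group, so single readings carry weight. Two programmers could also build different safety tables from the same SAP, one following 4.2 and the other 3.4.2.

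**Working it through.** No sample-size or power figure bears on this point. The check sets the passages side by side and counts the days that the windows cover.

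**1. Does the rule reach safety data?** Table 4.2 has a row for the follow-up period. Protocol 5.2.5 lists no efficacy test at that visit; its tests are safety assessments. The rule therefore covers safety visits. SAP 8.3 lifts the window for LOCF, and there is no matching exemption for safety.

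**2. Which safety tests are affected?**

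| Test | Protocol source | Default under SAP 4.2 |
|---|---|---|
| Any test at the extra visit after dose suspension | 7.1.2.1: "After dose suspension, an early subject visit other than the visits specified in this protocol will be scheduled" | Omitted if outside every window; if inside one, kept only if nearest the date |
| Follow-up laboratory tests | 5.1.9: "the laboratory value will be repeatedly evaluated until the value resolves to baseline level or becomes resolving" | Same |
| Same-day repeat vital signs | 5.1.7: "The measurement will be immediately repeated if any abnormality is observed" | Tie on date; the SAP does not say which value is kept |
| Discontinuation test | Table 1 Note 16, and 5.2.5 | Depends on timing; see step 4 |

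**3. Are there days outside every window?** From Table 4.2, ignoring the holiday extension for Day 15, the windows up to Day 169 are Days 3–5 (3 days), 6 (1), 15–20 (6), 24–34 (11), 50–64 (15), 78–92 (15), 120–134 (15) and 162–169 (8).

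- Days from Day 2 to Day 169: 169 − 2 + 1 = 168.
- ECG and vital signs: 3 + 1 + 6 + 11 + 15 + 15 + 15 + 8 = 74 days covered.
- Laboratory tests, not scheduled on Day 4: 74 − 3 = 71 days.
- Echocardiography, scheduled only at Days 85 and 169 in this span: 15 + 8 = 23 days.
- Longest gaps between windows: Days 93–119 (119 − 93 + 1 = 27 days) and Days 135–161 (161 − 135 + 1 = 27 days).

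This shows only that an off-schedule test can readily fall in no window. It counts calendar days, not tests.

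**4. The discontinuation test.** The follow-up row of Table 4.2 is 21 ± 7 days after the end of administration, that is 14 to 28 days. Protocol 5.2.5 gives the discontinuation test the same timing, which would place it in that row. Table 1 Note 16 instead places it at the first visit after discontinuation whenever possible. Take an assumed case with the last dose on Day 93 and the first visit on Day 100. The test is 100 − 93 = 7 days after the last dose, so it is outside 14–28 days, and Day 100 lies in the Day 93–119 gap. It would be omitted by default.

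**5. Do other outputs recover the values?** Partly.

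- Adverse-event and adverse-drug-reaction tables and listings cover everything arising or worsening after the first dose, with no visit window. Protocol 5.1.7 to 5.1.9 require clinically significant vital-sign, ECG, echocardiography and laboratory findings to be recorded as adverse events. The specified listing items include the event term and severity, but not the QTcF band or the measured value.
- SAP 6.2.2 plots each measured laboratory value by subject. Whether SAP 4.2 filters those plots is not stated.
- The abnormal-ECG and abnormal-echocardiography proportions are per subject. Whether SAP 4.2 applies to them is not stated.

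**The case against.** The strongest reply is that little of clinical importance can disappear. Findings judged clinically significant must enter the unwindowed adverse-event tables. A sodium below 130 mEq/L is a dose-suspension criterion in Protocol Table 7.1.2.1-1, so it should also appear among events leading to suspension. The exclusion is only a default, inclusion is possible if declared, and questionable data are settled with the medical expert before code breaking. SAP Section 7 also refers to an appendix list of standard analyses. The visible appendix holds only Tables 10.1 and 10.2, so further listings may exist. Finally, SAP 3.4.2 sits under a heading on missing and abnormal values, so its authors may not have had timing in mind.

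Most of this stands, and it rules out several stronger readings that a reader might infer.

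- *Off-schedule tests vanish from the safety analysis.* They do not: adverse-event and adverse-drug-reaction outputs are untouched.
- *The omission makes the drug look safer.* This is not shown. The extra visit after suspension checks whether an event has resolved or is resolving, and laboratory repeats continue until resolution, so many omitted values may be recovery values. Neither passage orders an extra ECG or echocardiogram.
- *More than half of such tests would be lost*, because 168 − 74 = 94 of 168 days lie outside the windows. Days are not tests, and the documents give no rate of unscheduled testing.
- *An abnormal-ECG count of 1/11 would become 0/11.* The SAP does not say that this proportion is windowed. It counts clinically significant changes, which must also be recorded as adverse events.

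What the reply leaves open is the numerical record. An adverse-event term does not show the QTcF band or laboratory value reached, and its capture depends on investigator judgement. The exception in SAP 4.2 has no criteria. Read literally, SAP 3.4.2 admits only clearly explained abnormal values as exclusions, so it does conflict with 4.2.

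**Conclusion.** The point holds as a gap in the data-handling rules for safety. By default, the QTcF-category, QTcF-change, laboratory, vital-sign and EF/FS summaries by time point omit three kinds of data: unscheduled tests outside the windows, repeats further from the stipulated date, and discontinuation tests done at a first visit that falls in no window. The two protocol timings for the discontinuation test need reconciling. The all-data statement in SAP 3.4.2 and Protocol 13.1.2.2 contradicts the default, and the visible SAP text offers no worst post-dose summary in its place.

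Neither the size nor the direction of any bias can be established from the documents. The conclusion assumes that SAP 4.2 is applied as written and that the appendix list contains no output that already uses unscheduled values. The change is still worth making before unblinding, because it uses data already collected and costs little.

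**What to change.** - In SAP 4.2, limit the exclusion and closest-date rules to by-visit summaries, and say which value counts when a measurement is repeated on the same day.
- State that the abnormal-ECG and abnormal-echocardiography proportions use all values after the first dose, including unscheduled, repeat and discontinuation tests.
- Add to the QTcF, QTcF-change and laboratory tables a row for the worst value after the first dose, one value per subject, drawn from the same full set of values.
- Reword SAP 3.4.2 and 4.2 so that they agree, and carry the same wording to Protocol 13.1.2.2 if it is amended.
- Reconcile Protocol Table 1 Note 16 with Protocol 5.2.5 on the timing of the discontinuation test, and give that test an explicit place in SAP Table 4.2.

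The cost is SAP wording and slight extra programming, with no new data or patients. The downside is that the added rows may look less favourable than the by-visit tables.

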#### 5. Primary Analysis

The following analyses will be performed for the primary endpoint, defined as the change from baseline in 6-minute walk distance (6MWD) at Week 24:

- (1) To evaluate the efficacy of TAS-205 appropriately, summary statistics will be calculated for each treatment group in the PPS.
- (2) As sensitivity analysis, the analysis described in (1) will be performed in the FAS.

#### 6. Secondary Analysis

Major items of secondary analysis in this study are shown below. Other items of standard analysis are shown in the list of the items of analysis.

#### **6.1** Analysis of the Primary Endpoint

The following analyses will be performed in the PPS and FAS:

The following analyses will be performed for the primary endpoint, defined as the change from baseline in 6MWD at Week 24: Analysis will also be conducted in the group combining the low-dose group and the high-dose group excluding the analysis of MMRM.

- A 2-sample t-test will be performed between each treatment group and placebo group. This analysis will be performed with and without the LOCF imputation. Analyses will also be conducted with the following baseline definitions.
  - (1) Analysis excluding the subjects for whom the value of (6MWD on Day 1 6MWD at screening)/6MWD at screening is 0.2 or higher or -0.2 or lower
  - (2) Analysis using the mean value of 6MWD on Day 1 and 6MWD at screening as the baseline value
- With respect to the above analysis, subgroup analysis will be conducted for the following items.

Subgroup analysis: Presence or absence of the history of steroid use, age category ( $\geq$ 5 years and <7 years, and  $\geq$ 7 years), and baseline 6MWD (<350 m, and  $\geq$ 350 m)

- The treatment effect will be estimated using the MMRM. The changes from baseline in 6MWD measured at other time points will also be included in this analysis. Covariates will be the assigned group, baseline value, time point, and the interaction term of the assigned group and time point.
- Using the MMRM, the dose relationship will be analyzed with treatment contrasts of (placebo group, low-dose group, high-dose group) = (-2 1 1), (-1 0 1), and (-1 -1 2). The changes from baseline in 6MWD measured at other time points will also be included in this analysis. Covariates will be the assigned group, baseline value, time point, and the interaction term of the assigned group and time point.
- For the above 2 analyses, analyses will be conducted in the PPS by adding age and the presence or absence of the history of steroid use to explanatory variables. In addition, subgroup analysis will be conducted for the following items.

Subgroup analysis: Baseline 6MWD ( $\leq$ 350 m, and  $\geq$ 350 m)

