# 3. Study Design

This study is a double-blind, randomized study to evaluate the efficacy of TAS-205 for deterioration of physical function (e.g., motor function, muscle volume, muscle strength) compared with placebo in patients with DMD; that is, the study is designed as an exploratory efficacy study.

The target total sample size of 33 patients will be obtained through central registration.

Subjects will be enrolled and randomized to low-dose group (6.67 to 13.33 mg/kg/dose), high-dose group (13.33 to 26.67 mg/kg/dose), or placebo group (randomization ratio: 1:1:1), and receive the investigational product orally twice daily, once after breakfast and once after dinner, for 24 consecutive weeks starting after dinner on Day 1 (subjects will be hospitalized on Day -2 within 12 days after enrollment and start Day 1 within 14 days after enrollment) to evaluate the efficacy in a double-blind manner. Subjects will receive the number of tablets per dose specified based on their body weights measured within 14 days before enrollment, as shown in Table 7.1.1-1.

The study design is shown in Figure 3-1 below.

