## 2. Target Sample Size and Rationale for the Sample Size

Target sample size: a total of 33 subjects (11 subjects for each group)

Given that DMD is a rare disease that allows only limited recruitment of subjects and that this study is primarily intended to evaluate the efficacy of TAS-205 in an exploratory manner, the sample size was determined not statistically, but based on feasibility.

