- (2) The following analyses will be performed for each value measured in each motor function test (time to rise from the floor test, Timed 10-m walk/run test, Timed Up & Go test), measurement of muscle volume (skeletal muscle CT, BIA), lean body mass, quantitative muscle strength assessments (hip flexion/extension, knee flexion/extension, ankle extension/flexion), serum CK concentration (only the serum CK concentration during the hospitalization period will be used for the efficacy evaluation), and pulmonary function test (VC, FVC, FEV1.0, FEV1.0%): In the analysis of the muscle volume measurement (skeletal muscle CT) in the PPS, the subjects of the reference values will be excluded. See Table 10.1 Method to Derive %MVI (%) for derivation of %MVI (%) of the muscle volume measurement (skeletal muscle CT). In quantitative muscle strength assessments, the maximum values in the measurement without compensation will be used.
  - Summary statistics will be calculated at each time point for each treatment group.
  - Summary statistics for the change from baseline will be calculated, followed by a 2-sample t-test between each treatment group and placebo group at each time point. The data at Week 24 will be analyzed with and without the LOCF imputation.
  - With respect to the above 2 analyses, subgroup analysis will be conducted for the following items.

Subgroup analysis: Presence or absence of the history of steroid use, age category ( $\geq$ 5 years and <7 years, and  $\geq$ 7 years), and baseline 6MWD (<350 m, and  $\geq$ 350 m)

- The treatment effect will be estimated at each time point using the MMRM. The changes from baseline in the values measured at other time points will also be included in this analysis. Covariates will be the assigned group, baseline value, time point, and the interaction term of the assigned group and time point.
- Using the MMRM, the dose relationship will be analyzed at each time point with treatment contrasts of (placebo group, low-dose group, high-dose group) = (-2 1 1), (-1 0 1), and (-1 -1 2). Covariates will be the assigned group, baseline value, time point, and the interaction term of the assigned group and time point.

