- For the above 2 analyses, %MVI (%) of muscular amount measurement (skeletal muscle CT) will be analyzed in the PPS by adding age and the presence or absence of the history of steroid use to explanatory variables. In addition, subgroup analysis will be conducted for the following items. Subgroup analysis: Baseline 6MWD (<350 m, and ≥350 m)

- The time course by each time point will be plotted for each treatment group. Similarly, changes in the muscle volume measurement (skeletal muscle CT) from baseline in the PPS will be plotted.

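### The SAP splits the Week 24 6MWD comparison by steroid history, age and walking level but never estimates how the treatment effect differs between the two halves of a split

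*SAP*

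**What the plan says.** The primary analysis (SAP 5) is summary statistics by group in the PPS, repeated in the FAS. The subgroup work is in the secondary analyses.

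- **SAP 6.1, t-tests.** "A 2-sample t-test will be performed between each treatment group and placebo group", with and without LOCF and under two alternative handlings of baseline. For the combined doses: "Analysis will also be conducted in the group combining the low-dose group and the high-dose group excluding the analysis of MMRM". These tests are then split: "With respect to the above analysis, subgroup analysis will be conducted for the following items". The factors are history of steroid use, age (5 to under 7 years, 7 years or older) and baseline 6MWD at 350 m.
- **SAP 6.1, MMRM.** The covariates are treatment, baseline value, time point and treatment by time point. Age and steroid history are added as explanatory variables in a PPS version. The subgroup refit is by baseline 6MWD only.
- **SAP 6.2.1.** For Week 12 6MWD and the other efficacy endpoints: "With respect to the above 2 analyses, subgroup analysis will be conducted for the following items". For %MVI from muscle CT, after the MMRM: "In addition, subgroup analysis will be conducted for the following items", again by the 350 m cut.
- **SAP 3.4.8** says that subgroup analyses are planned and leaves the method to the individual sections. **SAP 3.4.5** makes no multiplicity adjustment. The SAS code in **SAP 8.3** contains treatment by visit and no other interaction.
- **Size.** "Target sample size: a total of 33 subjects (11 subjects for each group"), and "the sample size was determined not statistically, but based on feasibility".

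The protocol's statistical section plans no subgroup analysis.

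**The concern.** A subgroup table invites one question: does the effect differ between boys who walk further and boys who walk less far, or between younger and older boys? Two p-values, one per subgroup, do not answer it. With five or six boys per arm each test has low power, so a uniform real effect can easily reach significance in one half and miss it in the other. The quantity that answers the question is the difference between the two effects with its confidence interval, and the SAP does not plan it for any factor.

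At stake is the interpretation of the secondary and exploratory output. The 350 m split recurs in SAP 6.1, 6.2.1, 6.3 and 6.6, so many tables will sit side by side with no measure of whether the two halves differ by more than chance.

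**Working it through.** **Is there a between-subgroup estimate anywhere?** SAP 3.4.8, 6.1, 6.2, 6.3, 6.6 and the code in 8.3 were read for a treatment-by-factor term, contrast or interval. The only interaction found is treatment by time point. Age and steroid history enter the MMRM without a product with treatment.

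**Inputs from the documents.** 33 boys, 11 per arm (SAP 2); equal allocation, "or placebo group (randomization ratio: 1:1:1") (Protocol 3); two-sample t-tests against placebo (SAP 6.1). The sample size rests on feasibility, so there is no power figure to reproduce.

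**Assumptions.** The documents give no effect, SD, subgroup size or alpha for the t-tests. Assumed here: 11 per arm splits 5/6 on each factor; two-sided 0.05; the same true effect d (in SD units) in both subgroups; one dose against placebo.

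**Formula.** The power in each subgroup comes from the noncentral t distribution with 2n − 2 df and noncentrality d/√(2/n). With powers p (n = 5 per arm) and q (n = 6 per arm), the chance that exactly one subgroup is significant is p(1 − q) + q(1 − p).

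| d | p (n = 5) | q (n = 6) | exactly one significant |
|---|---|---|---|
| 0 | 0.050 | 0.050 | 10% |
| 0.2 | 0.059 | 0.061 | 11% |
| 0.4 | 0.087 | 0.096 | 17% |
| 0.6 (30 m, SD 50 m) | 0.134 | 0.156 | 25% |
| 0.75 (30 m, SD 40 m) | 0.182 | 0.218 | 32% |
| 1.0 | 0.286 | 0.347 | 43% |
| 1.2 (60 m, SD 50 m) | 0.386 | 0.468 | 49% |
| 1.5 (60 m, SD 40 m) | 0.549 | 0.650 | 49% |
| 2.0 | 0.791 | 0.876 | 28% |

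Worked line, d = 1.2: 0.386 × 0.532 + 0.468 × 0.614 = 0.205 + 0.287 = 0.49. Both subgroups are significant in only 0.386 × 0.468 = 18% of trials.

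**Other splits.** For one dose against placebo, a 3/8 split gives 21% at d = 0.5, 47% at 1.0 and 62% at 1.5.

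**Interaction test, same conditions.** In simulation (1,500 trials per value of d, three independent 5/6 factors, and three comparisons: low, high and combined doses against placebo), a treatment-by-factor test was significant in 4.4–5.5% of comparisons at every d from 0 to 1.5. Over all nine factor-by-comparison pairs, at least one one-sided pattern appeared in 39% of trials at d = 0 and in 59–94% for d = 0.5–1.5. At least one significant interaction appeared in 24–28%.

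**Precision of the missing estimate.** For one dose against placebo, the SE of the difference in effects is SD × √(2/5 + 2/6) = 0.856 SD. The overall effect has SE SD × √(2/11) = 0.426 SD, about half as large. At an assumed SD of 50 m and with 33 − 6 = 27 df, the 95% half-width is 2.052 × 0.856 × 50 = 88 m.

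**The case against.** The strongest reply is that the plan never says how subgroup results are to be read. It sets no p-value rule, and Protocol 14.1 says that statistical significance of the 6MWD need not be determined and that efficacy is read on numerical trends. The 25–49% rates arise only for a reader who dichotomises at 0.05. For walking level, the MMRM refits also give estimates with 95% intervals. This stands in part: a reader might infer that the sponsor will judge subgroup differences from separate p-values alone, and the documents do not say so. But neither separate tests nor separate intervals give the difference, and with no reading rule the p-values are what readers will compare.

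Three further inferences should be resisted.

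- **The 350 m results will decide who enters the confirmatory study.** Protocol 14.2 mentions that study only for its planned 48-week evaluation. Nothing links subgroup results to later eligibility.
- **The 350 m cut throws away most of the information in baseline 6MWD.** A split at the median of a normally distributed modifier keeps about 64%, so the loss there is about a third. The documents do not say that 350 m is the median.
- **Separate refits are much less precise.** A refit of the three-arm MMRM draws its variance from all three arms. With about 11 and 14 df its within-subgroup half-widths at SD 50 m are about 70 and 62 m, against 65 and 59 m from one pooled model. Precision is not the argument.

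It is also fair to say that for a null or small effect the misleading pattern is much less frequent, and that 33 boys cannot support a firm statement about any interaction: 80% power would need a difference of about 2.5 SD.

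**Conclusion.** The concern holds as an omission from the secondary analyses. SAP 6.1 presents the Week 24 6MWD comparison in six subgroups defined by three factors and plans no estimate of how the effect differs within any factor. If the effect is in truth the same in both subgroups, separate tests give a one-sided pattern in about 10–17% of trials for d of 0–0.4 and 25–49% for d of 0.6–1.5, against about 5% for an interaction test. These figures are per factor and comparison. They rest on an assumed 5/6 split, two-sided 0.05 and assumed effects; PPS exclusions would make the subgroups smaller.

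The primary analysis is not affected, and the exploratory status limits the consequence to what the subgroup output can support. An interaction estimate would not make the subgroups informative; it would show how little they can say.

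**What to change.** **In SAP 6.1, for the Week 24 change in 6MWD**, add one model on all subjects for each factor:

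- Steroid history and age category: the planned MMRM plus factor, factor by visit, treatment by factor, and treatment by factor by visit.
- Walking level: the same structure with baseline 6MWD kept continuous. It is already a main effect, so the additions are its products with visit, with treatment, and with both.
- If the MMRM is unstable at this sample size, use a Week 24 ANCOVA with treatment by factor.

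Report the Week 24 difference in effect between subgroups with its 95% CI; for walking level, report it between two baseline distances stated in advance. Add a sentence that subgroup differences are read from this estimate and not from separate p-values. Keep the existing subgroup summaries as description, including the combined-dose, LOCF and alternative-baseline versions.

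**In SAP 6.2.1**, extend this only to selected endpoints. The listed items come to at least 17 (three timed tests, CT, BIA, lean body mass, six strength measures, CK, four lung function measures), so doing all of them in two analysis sets for three factors would need at least 17 × 2 × 3 = 102 fits. The walking-level modifier must be baseline 6MWD: BASE in the SAS code is the baseline of whichever endpoint is analysed. Skeletal muscle CT has one post-baseline measurement (Protocol Table 1), so use ANCOVA there.

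**Cost.** A few extra fits for 6MWD, and no new data, visits or subjects. The interval will be wide, about ±88 m for a binary 5/6 split at SD 50 m; the continuous walking-level term will have its own width. That width tells the reader that 33 boys cannot separate the subgroups.
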